4.2. Secondary endpoints

In relation to secondary objective 1:

Probe malfunction rate at the follow-up visit at M3 and M12 based on an abnormal impedance value (stimulation circuit and shock impedance) recorded during probe parameter testing.

In relation to secondary objectives 2 and 3:

Correlation between the probe malfunction rate and probe type and patient clinical variables.

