3.2. Secondary Objectives

The secondary objectives are to:

1. Determine the failure rates of defibrillation leads 3 and 12 months after the implantable device replacement.
2. Identify clinical variables that may be associated with a risk of failure.
3. Identify potential catheters at risk of failure.

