6.2.2. In the operating room

The procedure will be performed under general anesthesia or sedation, at the physician's discretion.

a) Before replacing the defibrillator's housing

Testing the lead parameters on the old defibrillator case

b) Replacement of the defibrillator housing

Replacement of the defibrillator housing and visual inspection of the connectors, following standard procedure.

After replacing the defibrillator housing

- Testing of probe parameters before and after connection to the new housing.
- Testing the defibrillation circuit:

Either via the standard defibrillation test, which involves inducing a ventricular arrhythmia through electrical cardiac stimulation and verifying the quality of its detection and the effectiveness of defibrillation.

Or via a high-energy synchronized shock; the test involves delivering a high-energy electrical shock synchronized with the QRS complex, in accordance with each manufacturer's standard guidelines (Appendix 1).

Important points:

- The use of an electrosurgical unit during surgery must be specified by the investigator, as its use may increase the risk of damaging the probe.
- If a malfunction of the defibrillation lead is detected during surgery, it will be replaced during the same procedure.

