6.2.4. Follow-up at 3 months and 1 year post-procedure

A standard follow-up visit to check the defibrillator is scheduled 3 months (\pm 3 months) and 12 months (\pm 3 months) after the procedure. This follow-up involves testing the lead's standard parameters (sensitivity, pacing threshold, pacing impedance, and defibrillation impedance), as well as downloading the device's memory to ensure there have been no abnormal signals from the lead since the procedure.

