6.3. Study Design

Steps	Inclusion Visit	In the operating room	3 months post-procedure (± 3 months)	12 months post-surgery (± 3 months)
	Pre-procedure Pre-procedure cardiology visit			
Information	R			
Consent	R			
Verification of criteria inclusion and non-inclusion	R			
Testing the probe settings on the old housing		R		
Replacing the defibrillator		S		
Visual inspection of the connectors		S		
Testing the probe parameters before and after connecting to the new housing		S		
Testing the defibrillation circuit on the new unit		R		
Test of probe parameters at 3 months (± 3 months) and 12 months (± 3 months) post-procedure			S	S
Recording of any complications		S	S	S

R: Procedures, processes, and treatments added by the research;

S: Procedures, processes, and treatments related to care

6.4. Expected duration of participant involvement, description of the timeline and duration of the study

The study for a patient begins when the patient and the investigator sign the consent form and ends at the 12±3-month visit. For each patient, the duration of the study will therefore be 12 months (± 3 months).

The planned enrollment period is 24 months. The study is expected to take 39 months to complete, starting from the date of the first enrollment.

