8. STATISTICAL

8.1. Description of planned statistical methods

Study population

All included subjects will be included in the analyses, which will be conducted according to the ITT principle.

Statistical analyses

An initial analysis of the data will provide a description of the overall population. The normality of the distribution of quantitative variables will be assessed using the Shapiro-Wilks normality test. Statistical results will be presented as means \pm standard deviations for quantitative variables with a Gaussian distribution, and as medians and interquartile ranges for other variables. For qualitative variables, frequencies and associated percentages will be presented. Qualitative variables will be compared using a chi-square test. If the conditions for conducting this test are not met, Fisher's exact test will be used. Quantitative variables will be compared between the two groups: for normally distributed variables, using a Student's t-test or an analysis of variance; for non-normally distributed variables, using a Wilcoxon-Mann-Whitney test.

Analysis of the primary outcome measure

Dysfunction rates will be estimated as point estimates and 95% confidence intervals.

Analysis of Secondary Endpoints

Depending on the rates of dysfunction observed, logistic regression will be used to estimate the variables associated with the risk of dysfunction. If the rate is too low for such modeling, descriptive analyses will be performed.

Modeling of dysfunction times over time may be performed using a Kaplan-Meier model. A Cox regression may be adjusted to determine the associated variables.

8.2. Expected number of participants to be included in the study, with statistical justification

Since the primary objective is to detect a non-zero rate of probe malfunction at the time of the procedure, we base the calculation of the sample size on the binomial distribution and the probability of observing no malfunctions in a sample of size n . Assuming a minimum malfunction rate of 1%, a study of 299 subjects yields a probability of observing no malfunctions that is less than an alpha risk of 5%. To account for unusable data and withdrawals of consent, we propose including a total of $N=330$ subjects in this study.

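### The month-3 and month-12 lead failure rates count only what the visit test finds, so a lead that failed and was dealt with before the visit is not captured

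*Combined protocol and SAP*

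**What the plan says.** All references are to the combined protocol and SAP.

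- **Objective (3.2):** "Determine the failure rates of defibrillation leads 3 and 12 months after the implantable device replacement".
- **Endpoint (4.2):** "Probe malfunction rate at the follow-up visit at M3 and M12 based on an abnormal impedance value". Both stimulation-circuit and shock impedance qualify, and the value is the one "recorded during probe parameter testing". The primary endpoint (4.1) uses shock impedance only.
- **Visit content (6.2.4):** the lead parameter test is listed first. The download of the device's "memory to ensure there have been no abnormal signals from the lead since the procedure" is added as a separate item.
- **Schedule (6.3):** "Test of probe parameters at 3 months (± 3 months) and 12 months (± 3 months) post-procedure". Complications are also to be recorded at both visits.
- **Data list (12.5):** the only postoperative item is the lead parameter test result. Complications appear under intraoperative data. No failure date, memory finding or lead revision is listed.
- **Leads replaced at surgery (6.2.2):** "If a malfunction of the defibrillation lead is detected during surgery, it will be replaced during the same procedure". Section 8.1 analyses every included subject and has no rule for replaced leads.
- **Time-to-event analysis (8.1):** "Modeling of dysfunction times over time may be performed using a Kaplan-Meier model". It is optional, and no origin, event date or censoring rule is given.

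**The concern.** The objective is about what happens to leads over 3 and 12 months. The endpoint records what is wrong with them on one day. The two agree only if every failure is still in place, and still shows an abnormal impedance, when the patient is seen.

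That is unlikely to hold throughout. Section 2.1 itself says that telemetry allows lead malfunctions to be found early, so some failures will plausibly be acted on between visits. Those leads are the clearest failures in the study, and the definition leaves them out.

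Only about 10 to 12 failures would be expected by one year at the cited 3.5%, so losing a few changes the result. The same malfunction rate feeds objectives 2 and 3 (clinical variables and lead types at risk), which would lose the same events. Because the data list has no date or revision field, the loss may not be recoverable at analysis.

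**Working it through.** **1. The plan's own figure.** None is stated for the follow-up endpoint. The sample size in 8.2 concerns the intraoperative endpoint and reproduces: 0.99^298 = 0.05004 and 0.99^299 = 0.04954, so 299 is the smallest n with a probability of no malfunction below 5%. Nothing below changes it.

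**2. What happens to a lead that fails at month 2 and is replaced at month 2.5.** At the month-3 visit the test is made on the new lead and is normal, or there is no value for the original lead. In neither case is there an abnormal impedance at the visit, so section 4.2 yields no event. The memory may show the fault, but 4.2 does not draw on it.

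**3. Size of the undercount.** Inputs: true one-year rate p = 3.5% (2.1, a background figure used for illustration); f = share of failures acted on before the visit (assumption, since the documents give no value). All other failures are taken to show on the visit test.

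- If the patient tests normal: reported rate = p(1 − f).
- If the patient is treated as missing: reported rate = p(1 − f) / (1 − pf).

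| f | tests normal | missing | events counted of 330 × 0.035 = 11.6 |
|---|---|---|---|
| 0 | 3.5% | 3.5% | 11.6 |
| 25% | 2.6% | 2.6% | 8.7 |
| 50% | 1.75% | 1.78% | 5.8 |
| 75% | 0.9% | 0.9% | 2.9 |

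With 299 patients the true expected count is 299 × 0.035 = 10.5. Treating these patients as missing barely helps, because the event is lost either way. Failures that show only in memory would add to the loss and are not quantified here.

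**4. Windows.** 3 ± 3 months is month 0 to 6; 12 ± 3 is month 9 to 15. With a constant hazard h = −ln(1 − 0.035) = 0.0356 per year (assumption), cumulative risk 1 − exp(−ht) is:

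| month | 0 | 3 | 6 | 9 | 12 | 15 |
|---|---|---|---|---|---|---|
| risk | 0% | 0.89% | 1.77% | 2.64% | 3.50% | 4.36% |

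These are the extremes for patients all seen at one end of a window. If visits are spread evenly, the averages are about 0.89% and 3.50%, the target values. The windows blur the time point without a fixed direction.

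**5. Leads replaced at surgery.** At the 1% design rate, 299 × 0.01 ≈ 3 patients carry a new lead into follow-up. Removing them moves 10.5/299 = 3.51% to 10.5/296 = 3.55%, which is negligible.

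**6. Definitions.** Shock impedance alone at surgery (4.1), and shock or stimulation-circuit impedance at follow-up (4.2). The two rates do not measure the same thing.

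**The case against.** The strongest reply is that the protocol never says a replaced lead scores as normal. It is silent, and a site could report the patient as a malfunction or leave the value missing. Section 6.3 records complications at both visits, which could pick up a lead revision, and 8.1 foresees Kaplan-Meier and Cox models, which need dated events. This is a secondary, descriptive rate with about 10 events; the exact 95% interval for 10 of 299 is 1.6% to 6.1%.

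The silence is real: scoring as normal is a consequence of the wording, not a stated rule. But the wording still gives no route by which the event counts. The complications record is not linked to the endpoint and is missing from the postoperative data list, and the survival analysis is optional with no dates behind it. These safeguards narrow the gap without closing it. A wide interval does not excuse a systematic loss.

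Several stronger readings are tempting and are not supported:

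- **That every feature here biases the rate downward.** The windows have no fixed direction, and adding the stimulation circuit can only add events.
- **That a pacing-circuit fault present at surgery would surface as a new failure at month 3.** Section 6.2.2 tests lead parameters on the old housing and before and after connection to the new one, and its replacement rule is not limited to shock impedance. Such a fault should be seen then.
- **That failures generally cluster within 3 months.** Section 2.1 reports that apparent peak for one recalled lead model only.
- **That the reported rate will be half the true one.** That needs f = 50%, which no passage supports.

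**Conclusion.** The point holds for the endpoint definition. As written, the month-3 and month-12 rates leave out failures acted on before the visit and failures visible only in device memory, so they understate the failure rate that objective 1 asks for. The direction follows from the wording. The size is not known: at a true 3.5% it runs from no loss at f = 0 to a reported 0.9% at f = 75%, and both the 3.5% and f are illustrative.

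Three lesser points stand. The rates are not for a common time point; leads replaced at surgery stay in the denominator, with negligible effect; and the follow-up definition is broader than the primary one, so the two rates cannot be compared directly. The primary endpoint, 299 and 330 are untouched.

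**What to change.** - **Endpoint:** cumulative failure of the original lead since the procedure. An event is abnormal pacing or shock impedance at a visit, a lead-failure signal in device memory (defined in advance for each manufacturer), or lead revision or replacement for malfunction.
- **Data:** add eCRF fields for event date and lead revision.
- **Risk set:** patients who leave surgery with the original lead. Intraoperative failures remain in the primary endpoint.
- **Estimate:** make the Kaplan-Meier analysis already foreseen in 8.1 the planned one, read at 3 and 12 months from actual dates, with the origin and censoring rule stated.
- **Comparison with surgery:** tabulate shock-circuit failures separately, so that they can be set beside the intraoperative rate.

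The cost is a few eCRF fields and the work of agreeing the memory-signal definition across the five manufacturers in Appendix 1. The memory is already downloaded, and visits, procedures and sample size do not change.

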5. SELECTION OF RESEARCH PARTICIPANTS

5.1. Inclusion Criteria

The following patients will be included:

- Over 18 years of age,
- Who have a VVI, DDD, or BiV defibrillator implanted and require a device replacement due to battery wear,
- Who have given their consent to participate in accordance with regulations,
- Currently enrolled in a social security program or eligible for coverage.

5.2. Exclusion criteria

Patients meeting the following criteria will not be included:

- Atrial fibrillation (AF) without effective anticoagulation for a shock,
- Severe aortic stenosis,
- Stroke occurring within the month prior to enrollment,
- Hemodynamic instability contraindicating shock therapy,
- Contraindication to anesthesia,
- Pregnant or breastfeeding women,
- Inability to understand the information provided,
- Under guardianship, conservatorship, or judicial protection.

5.3. Exclusion criteria

No exclusion criteria.

5.4. Recruitment Criteria

All patients scheduled for a defibrillator enclosure replacement who meet the eligibility criteria will be offered the opportunity to participate in the study. They will be informed during the pre-procedure cardiology consultation. Informed consent will be obtained after taking the time to verify that the information provided has been fully understood. Patients unable to understand the content of the information provided will not be included in the study.

5.5. Simultaneous Participation in Another Study, Exclusion Period

Patients may participate in another study simultaneously provided that the inclusion and exclusion criteria are met. There is no exclusion period for participants in this study.

6. RESEARCH METHODOLOGY

6.1. Study Type

Interventional, multicenter, prospective, non-randomized, open-label study.

6.2. Study Protocol

6.2.1. Inclusion

The patient will be informed of the protocol by an investigator during the pre-procedure cardiology consultation. Clear and honest information will be provided to the patient both verbally and in writing (see information sheet). The physician will verify the inclusion and exclusion criteria.

If the patient agrees to participate in the study after a cooling-off period that he or she considers sufficient, a consent form will be provided. This form must then be dated and signed by the investigator and the patient.

6.2.2. In the operating room

The procedure will be performed under general anesthesia or sedation, at the physician's discretion.

a) Before replacing the defibrillator's housing

Testing the lead parameters on the old defibrillator case

b) Replacement of the defibrillator housing

Replacement of the defibrillator housing and visual inspection of the connectors, following standard procedure.

After replacing the defibrillator housing

- Testing of probe parameters before and after connection to the new housing.
- Testing the defibrillation circuit:

Either via the standard defibrillation test, which involves inducing a ventricular arrhythmia through electrical cardiac stimulation and verifying the quality of its detection and the effectiveness of defibrillation.

Or via a high-energy synchronized shock; the test involves delivering a high-energy electrical shock synchronized with the QRS complex, in accordance with each manufacturer's standard guidelines (Appendix 1).

Important points:

- The use of an electrosurgical unit during surgery must be specified by the investigator, as its use may increase the risk of damaging the probe.
- If a malfunction of the defibrillation lead is detected during surgery, it will be replaced during the same procedure.

6.2.3. In the post-operative monitoring room / On the ward

Recording of any complications

6.2.4. Follow-up at 3 months and 1 year post-procedure

A standard follow-up visit to check the defibrillator is scheduled 3 months (\pm 3 months) and 12 months (\pm 3 months) after the procedure. This follow-up involves testing the lead's standard parameters (sensitivity, pacing threshold, pacing impedance, and defibrillation impedance), as well as downloading the device's memory to ensure there have been no abnormal signals from the lead since the procedure.

6.3. Study Design

Steps	Inclusion Visit	In the operating room	3 months post-procedure (± 3 months)	12 months post-surgery (± 3 months)
	Pre-procedure Pre-procedure cardiology visit			
Information	R			
Consent	R			
Verification of criteria inclusion and non-inclusion	R			
Testing the probe settings on the old housing		R		
Replacing the defibrillator		S		
Visual inspection of the connectors		S		
Testing the probe parameters before and after connecting to the new housing		S		
Testing the defibrillation circuit on the new unit		R		
Test of probe parameters at 3 months (± 3 months) and 12 months (± 3 months) post-procedure			S	S
Recording of any complications		S	S	S

R: Procedures, processes, and treatments added by the research;

S: Procedures, processes, and treatments related to care

6.4. Expected duration of participant involvement, description of the timeline and duration of the study

The study for a patient begins when the patient and the investigator sign the consent form and ends at the 12±3-month visit. For each patient, the duration of the study will therefore be 12 months (± 3 months).

The planned enrollment period is 24 months. The study is expected to take 39 months to complete, starting from the date of the first enrollment.

6.5. Identification of Participants

For this study, participants will be identified as follows:

Upon signing the consent form, the investigator will log into the eCRF and create a patient record. The presence of inclusion criteria and the absence of exclusion criteria will be verified on the site prior to assigning an enrollment number in order to minimize the possibility of selection bias. The alphanumeric “patient identifier” enrollment number will then be automatically generated by the application. It consists of the center number followed by a sequential enrollment number and the patient’s initials (first letter of the last name and first letter of the first name). This unique identifier will be retained for the duration of the study.

The principal investigator establishes and maintains a list of patients enrolled in the study. This list allows for the unambiguous association of the patient’s identity with their enrollment number.

6.6. Description of measures taken to reduce or avoid bias

6.6.1. Patient selection

To avoid any selection bias, this study will be offered to all patients scheduled for a defibrillator device replacement who meet the inclusion and exclusion criteria assessed during the pre-procedure cardiology consultation. For eligible patients who are not included, the reason for exclusion will be noted.

6.6.2. Blinding procedures, measures implemented to maintain blinding, and procedures for unblinding, if applicable

N/A

6.7. Description of the rules for permanent or temporary withdrawal of a person's participation in the research, procedures for monitoring these individuals, and procedures for replacing these subjects, if applicable

Any subject included in the study may at any time decide to withdraw their consent to participate, for any reason, without having to provide explanations or justifications and without this affecting the care they are receiving or will receive. The investigator must indicate in the patient's eCRF the date and, if applicable, the reason for discontinuation of participation in the research. Withdrawal of consent prohibits the use of medical data obtained after the withdrawal of consent. Data already collected regarding the subject may be used, unless the patient objects.

The investigator may temporarily or permanently discontinue a subject's participation in the study for any reason that affects the subject's safety and in the best interests of the patient. Data already collected regarding the subject may be used in the analysis of the study results.

A subject's withdrawal from the study will not affect their usual care.

A patient who withdraws prematurely from the study will be replaced, and a study withdrawal form will be completed, including, if possible, the reason for withdrawal (Consort flow diagram).

Once the protocol-specified sample size is reached, the investigator must halt recruitment for the study. However, patients who have already signed a consent form may still be included in the study.

6.8. Identification of all data collected directly in the study's eCRF and for which no other source documents exist

NA

7. SAFETY ASSESSMENT

In the context of interventional research involving minimal risk and constraints, the medical procedures or strategies that are the subject of the research are part of standard practice and are used in accordance with their indications. Potential incidents or adverse events are therefore those related to the patient's routine care (care-related) and do not require a specific report from the research manager.

These events must follow the standard reporting procedure established by current regulations and implemented at the facility:

- Adverse effects that may be related to a medication, to be reported to the Regional Pharmacovigilance Center,

- Incidents or potential incidents resulting from the use of a medical device to be reported to the local medical device vigilance liaison,
- Others (reporting of nosocomial infections).

These reports are mandatory for all physicians (or other relevant healthcare professionals), both within the context of this research and outside of it.

